34. **Concomitant Treatments:** All concomitant medications and Non-Drug Supportive Interventions should be recorded in the CRF. See Section 5.4 for additional information.
35. **Mandatory FFPE Tumor Tissue:** A mandatory archived formalin-fixed, paraffin-embedded (FFPE) tumor tissue block must be provided that is of sufficient size to allow for sectioning of ten (10) 5-micron tissue sections. If an FFPE tumor tissue block cannot be provided, sites should provide, preferably, fifteen (15), but a minimum of ten (10), unstained slides each containing a 5-micron tissue section cut serially from the same FFPE block. If tissue from multiple surgeries is available, the most recent specimen should be submitted. If archived FFPE tissue is not available, a de novo (ie, fresh) tumor sample **must** be obtained in accord with local institutional practice for tumor biopsies. Archived or de novo tumor tissue from cytologic sampling (eg, fine needle aspiration, including FFPE cell pellet material) is not adequate and should not be submitted. See Sections 6.1.1 and Section 7.4.
36. **De Novo Tumor Tissue:** In addition to the archival specimen a de novo (ie, fresh biopsy) tumor sample must be collected prior to enrollment unless clinically contraindicated. An optional de novo tumor sample is encouraged to be collected at End of Treatment if a patient discontinues due to disease progression. Tumor tissue from cytologic sampling (eg, fine needle aspiration, including FFPE cell pellet material), is not adequate and should not be submitted. See Section 6.1.1 and Section 7.4.1.
37. **Banked Blood Biospecimens:** Blood biospecimens will be collected from patients at Screening (4 mL) and 20.5 mL will be collected before the start of the first infusion on Cycle 1, Day 1 and Day 15; Cycle 2, Day 1; Cycle 3, Day 1; and at End of Treatment. The biospecimens will be retained for potential pharmacogenomic/biomarker analyses related to drug response, unless prohibited by local regulations or ethics committee decision. Patients also have the choice to allow these specimens to be used in research on additional topics. See Sections 7.5.1 and 7.5.2.

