- Patients will be stratified according to platinum-refractory or platinum-resistant status, number of prior regimens (1 vs 2 or 3), and bulky disease (defined as presence of a tumor ≥ 5 cm) vs not.
- The final analysis of this study has been completed; however, this study will remain open to allow the remaining patients currently enrolled in Arm A or Arm B to continue receiving avelumab as a single agent or in combination with PLD. These patients will be allowed to continue receiving avelumab based on the investigator's assessment that the anticipated benefit outweighs the risks.
- The schedule of activities (SOA) found in [Appendix 7](#) is replacing the previous SOA and has been revised to decrease the frequency of study procedures while maintaining appropriate assessment of patient safety.

Study Treatments

Avelumab (Arm A, Arm B) 10 mg/kg will be given as a 1-hour intravenous infusion (IV) every 2 weeks (Q2W) in 4-week cycles.

PLD (Arm B, Arm C) 40 mg/m² will be given as a 1-hour IV infusion every 4 weeks (Q4W) in 4-week cycles.

In all patients, study treatment may continue until PD as assessed by the investigator, unacceptable toxicity, patient refusal, patient loss to follow up, or termination of the study by the Sponsor, whichever comes first (see [Section 6.5](#) Withdrawal). Avelumab and PLD will not be continued beyond disease progression. Patients who are on single-agent avelumab post-progression at the time of amendment approval will be discontinued from avelumab after documentation of a subsequent disease progression. Cross-over will not be permitted. Patients on Arm B who are discontinued from avelumab treatment for any reason, must also be discontinued from PLD (within the scope of this study, if applicable) and entered into the 90 Day Safety Follow-up Period.

Statistical Methods

Sample Size Determination

The primary objectives of this study are to demonstrate that avelumab given alone or in combination with PLD is superior to PLD alone in prolonging OS or PFS in patients with platinum-resistant/refractory ovarian cancer. The study is designed to test in parallel four hypotheses.

- The first null hypothesis is that the true OS hazard rates for PLD alone and avelumab alone arms are the same ($HR=1$) versus the alternative hypothesis that the true hazard rate is smaller in the avelumab alone arm than in the PLD alone arm ($HR<1$).

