5. **Safety Follow-up:** All patient safety follow-up visits are scheduled monthly for 90 days after the last dose of study treatment (Day 30 \pm 3, Day 60 \pm 3, Day 90 \pm 3). Final visit is scheduled to occur at least 90 days, and no more than 93 days, after the last dose of study treatment. PK sample collection is only required at the first follow-up visit (Day 30).
6. **Follow-up for PFS and OS:** Patients without evidence of disease progression at the time of treatment discontinuation should remain on the study and continue to have tumor assessment radiological scans every 8 weeks until documented progressive disease. Patients who have discontinued study treatment due to progressive disease should be followed for survival every 12 weeks via telephone call until study end. Additionally, subsequent anti-cancer therapies, surgery, and date of initiation and discontinuation of each anti-cancer drug will be recorded in the CRF.
7. **Informed Consent:** Must be obtained prior to undergoing any study-specific procedures.
8. **Tumor History:** Includes collection of tumor history, prior antitumor regimen(s), including treatment duration and best response observed.
9. **Physical Examination:** Includes an examination of major body systems, and weight (height included at screening only). Abnormal findings identified prior to first dose of study treatment should be documented in medical history.
10. **Baseline Signs & Symptoms:** Patients will be asked about any signs and symptoms experienced within the 14 days prior to study enrollment. Baseline signs and symptoms will be recorded on the Medical History case report form (CRF) page.
11. **Vital Signs:** Blood pressure (BP) and pulse rate should be taken before any other assessments (eg, PK, laboratory blood draws) with the patient in the seated position after the patient has been sitting quietly for at least 5 minutes.
12. **ECOG Performance status:** Use Eastern Cooperative Oncology Group (ECOG) – see [Appendix 2](#).

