30. **Premedications:** For additional information about premedications for PLD and avelumab, see [Section 5.2.3.1](#) and [Section 5.2.3.3](#).

31. **Tumor Assessments:** Tumor assessments will include all known or suspected disease sites. Tumor assessments must include chest, abdomen and pelvis CT or MRI scans and will be conducted every 8 weeks until documented disease progression as assessed by BICR regardless of subsequent anti-cancer therapy. Brain scans will be performed at baseline only if disease is suspected and on study as appropriate to follow disease. Baseline central nervous system (CNS) imaging is not required with the exception of symptomatic patients to rule out CNS metastases. A bone scan (bone scintigraphy) or ¹⁸F-FDG-PET/CT is required at baseline only if disease is suspected and then every 16 weeks only if bone metastases are present at baseline. Otherwise, bone imaging is required only if new bone metastases are suspected. Bone imaging is also required at the time of CR confirmation for patients who have bone metastases. MRI is acceptable for bone imaging if consistent with local practice. CT or MRI scans to be done every 2 cycles (every 8 weeks) (window of 5 days prior to dosing is allowed) throughout the study. In case partial response (PR), complete response (CR) or Progressive Disease (PD) is observed according to RECIST v.1.1 (Appendix 3) and CCI (Appendix 4) (Nishino 2014),⁴⁹ confirmation CT or MRI should be performed no sooner than 4 weeks after the first documentation of response. Tumor assessment should be repeated at the End of Study visit if more than 4 weeks have passed since the last evaluation. All radiographic images will be collected and will be objectively verified by a BICR independent third-party core imaging laboratory as described in Study Manual. See Section 7.6 for additional information.
32. **Patient-Reported Outcome Questionnaire:** EORTC QLQ-C30, EORTC QLQ-OV28, and EQ-5D-5L are to be administered on Day 1 of Cycle 1, Day 1 of each subsequent cycle, End of Treatment/Withdrawal Visit and the 30, 60 and 90 day Safety Follow-up visits prior to any study or medical procedure. See Appendix 6.
33. **Adverse Event (AE) Assessments:** Adverse events should be documented and recorded in the CRF. The National Cancer Institute Common Terminology Criteria for Adverse Events (NCI CTCAE) version (v) 4.03 will be used. (Appendix 5). See Section 8.2 for Reporting Period details.

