If the true HR is 0.6 under the alternative hypothesis, 196 OS events within each comparison will be required to have 90% power to detect a HR of 0.6 using a one-sided log rank test at a significance level of 0.0115 (overall significance level in the study one-sided 0.025), and a 2-look group sequential design with Lan-DeMets (O'Brien-Fleming) α -spending function to

determine the efficacy boundary and a Gamma Family (-10) β -spending function to determine the non-binding futility boundary

- PFS

It is assumed that the median PFS for patients receiving PLD is 3.5 months,²⁴ and that treatment with avelumab alone or avelumab in combination with PLD is expected to increase the median PFS to 5.8 months, corresponding to a hazard ratio (HR) of 0.6 under the exponential model assumption. The sample size further assumes a 15% drop-out rate within each arm, and non-uniform patient accrual over a 19-month period and minimum follow-up of 12 months after the last patient is randomized.

If the true HR is 0.6 under the alternative hypothesis, 325 PFS events by BICR assessment within each comparison will provide 93% power to detect a HR of 0.6 using a one-sided log rank test at a significance level of 0.001 (overall significance level in the study one-sided 0.025), and a 2-look group sequential design with Lan-DeMets (O'Brien-Fleming) α -spending function to determine the efficacy boundary and a Gamma Family (-10) β -spending function to determine the non-binding futility boundary.

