5. GENERAL METHODOLOGY AND CONVENTIONS

5.1. Hypotheses and Decision Rules

5.1.1. Hypotheses and sample size determination

The study is designed to test, in parallel, the following hypotheses:

$$H_{01}: HR_{OS(avelumab/PLD)} \geq 1, \text{ versus } H_{a1}: HR_{OS(avelumab/PLD)} < 1$$

$$H_{02}: HR_{OS(avelumab+PLD/PLD)} \geq 1, \text{ versus } H_{a2}: HR_{OS(avelumab+PLD/PLD)} < 1$$

$$H_{03}: HR_{PFS(avelumab/PLD)} \geq 1, \text{ versus } H_{a3}: HR_{PFS(avelumab/PLD)} < 1$$

$$H_{04}: HR_{PFS(avelumab+PLD/PLD)} \geq 1, \text{ versus } H_{a4}: HR_{PFS(avelumab+PLD/PLD)} < 1$$

where HR_{OS} represents the hazard ratio for OS in each of the experimental arms vs the control arm, and HR_{PFS} represents the hazard ratio for PFS by BICR assessment in each of the experimental arms vs the control arm.

The treatment effects on the primary PRO endpoint, time to deterioration (TTD), will also be tested.

$$H_{05}: HR_{TTD(avelumab/PLD)} \geq 1, \text{ versus } H_{a5}: HR_{TTD(avelumab/PLD)} < 1$$

[figure not shown]
$$H_{06}: HR_{TTD(avelumab+PLD/PLD)} \geq 1, \text{ versus } H_{a6}: HR_{TTD(avelumab+PLD/PLD)} < 1$$

where HR_{TTD} represents the hazard ratio for TTD in each of the experimental arms vs the control arm.

Approximately 550 patients will be randomized to the treatment arms using a 1:1:1 randomization, stratified by platinum-refractory or platinum-resistant status, number of prior regimens (1 vs 2 or 3), and bulky disease (defined as presence of a tumor ≥ 5 cm) vs not.

Overall type I-error will be maintained at or below 1-sided 0.025 by allocating 0.0115 alpha to each of the two OS comparisons and 0.001 to each of the two PFS comparisons. A gatekeeping procedure will be used to allow further testing of TTD for patients as described in Figure 1. The significance levels for each test will also take into account the group sequential nature of the design.

Figure 1 Testing Strategy

For each of the two OS comparisons, 196 OS events will be required to have at least 90% power to detect a hazard ratio of 0.6 using a 1-sided log-rank test at a significance level of 0.0115, and a 2-look group-sequential design with Lan-DeMets (O'Brien-Fleming) α -spending function to determine the efficacy boundary and a Gamma Family (-10) β -spending function to determine the non-binding futility boundary.

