5.1.2. Decision rules

OS

To protect the integrity of the study and to preserve the type I error rate, a fraction of alpha (0.002) for OS efficacy will be spent at the interim analysis and accounted for in the overall type I error rate if the interim analysis is performed at the planned number of OS events. The nominal significance levels for the interim and final efficacy analyses of OS will be determined by using the Lan-DeMets procedure with an O'Brien-Fleming stopping boundary. The overall significance level for the efficacy analysis of OS, within each comparison, will be preserved at 0.0115 (1-sided).

Two analyses will be performed for OS:

1. an interim analysis will be conducted after all patients have been randomized in the study and at least 131 (67%) of the 196 OS events for each of the OS comparisons have been documented and
2. the final analysis for OS will be conducted after all patients randomized in the study have been followed for 12 months and at least 196 OS events for each of the OS comparisons have been documented.

PFS based on BICR assessment

All references to PFS in this section pertain to PFS based on BICR assessment even when not specifically stated.

A fraction of alpha (0.0003) for PFS efficacy will be spent at the interim analysis and accounted for in the overall type I error rate if the interim analysis is performed at the planned number of PFS events. The nominal significance levels for the interim and final efficacy analyses of PFS will be determined by using the Lan-DeMets procedure with an O'Brien-Fleming stopping boundary. The overall significance level for the efficacy analysis of PFS, within each comparison, will be preserved at 0.001 (1-sided).

Two analyses will be performed for PFS:

1. an interim analysis will be conducted after all patients have been randomized in the study and at least 267 (82%) of the 325 PFS events for each of the PFS comparisons have been documented based on BICR assessment, and
2. the final analysis for PFS after all patients randomized in the study have been followed for 12 months and at least 325 PFS events for each of the PFS comparisons have been documented based on BICR assessment.

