6.1.2. Progression-free survival as assessed by BICR per RECIST v1.1

6.1.2.1. Primary analysis

The following analyses will be based on the FAS using the strata assigned at randomization. Progression of disease (PD) below refers to PD by BICR assessment.

Progression-Free Survival (PFS) is defined as the time from date of randomization to the date of the first documentation of PD or death due to any cause, whichever occurs first.

PFS data will be censored on the date of the last adequate tumor assessment for patients who do not have an event (PD or death), for patients who start a new anti-cancer therapy prior to an event (see Section 5.2.6) or for patients with an event after 2 or more missing tumor assessments. Patients who do not have an adequate baseline tumor assessment or who do not have an adequate post-baseline tumor assessment will be censored on the date of randomization unless death occurred on or before the time of the second planned tumor assessment (ie, \leq 16 weeks after the date of randomization) in which case the death will be considered an event.

090177e19142bcd4\Approved\Approved On: 09-Jul-2019 05:44 (GMT)

In this study antitumor activity will be assessed through radiological tumor assessments conducted at screening and every 8 weeks until disease progression regardless of initiation of subsequent anti-cancer therapy. The allowable time window for disease assessments is 5 days prior to dosing while on treatment and whenever disease progression is suspected (eg, symptomatic deterioration).

The censoring and event date options to be considered for the PFS and DR analysis are presented in Table 9.

$$\text{PFS (months)} = [\text{date of event or censoring} - \text{date of randomization} + 1] / 30.4375$$

Table 9. Outcome and event dates for PFS and DR analyses

Scenario	Date of event/censoring	Outcome
No adequate baseline assessment	Date of randomization ^a	Censored ^a
PD or death - After at most one missing or inadequate post-baseline tumor assessment, OR - ≤ 16 weeks after the date of randomization	Date of PD or death	Event
PD or death - after 2 or more missing or inadequate post-baseline tumor assessments	Date of last adequate tumor assessment ^b documenting no PD before new anti-cancer therapy is given or missed tumor assessments	Censored
No PD and no death	Date of last adequate tumor assessment ^b documenting no PD before new anti-cancer therapy is given or missed tumor assessments	Censored

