6.2.2.2. Sensitivity analyses for progression-free survival

The following sensitivity analyses will be performed to explore the robustness of the primary analysis results. These analyses are regarded as purely exploratory. The sensitivity analyses will repeat the primary analysis (p-value, HR and 95% CIs) described in Section 6.1.2.1 with the modifications below:

- PFS based on BICR assessment and counting all PD and deaths as events regardless of missing assessments or timing of the event
- PFS based on BICR assessment on the PP analysis set for PFS
- PFS based on BICR assessment using an unstratified analysis
- PFS based on BICR assessment using strata derived according to eCRF data instead of those entered in IRT. See Section 6.2.2.1 for the derivation associated with the stratification factor of bulky disease.
- PFS based on BICR assessment modifying the censoring rules in Table 9 to consider all deaths as events
- PFS based on BICR assessment modifying the censoring rules in Table 9 with initiation of subsequent anti-cancer therapies not used as a censoring reason

Methods for evaluating the validity of model assumptions

The same methodology described in Section 6.2.2.1 for OS will be used for PFS based on BICR assessment.

BICR vs Investigator assessment

A summary of the BICR assessment versus investigator assessment will be provided including numbers of concordant and discordant assessments as well as the number of cases where PFS event was assessed at different timepoints based on BICR and investigator assessments.

Table 11 outlines the possible outcomes by investigator and BICR (Amit et al. 2011).

Table 11. Possible Outcomes for Investigator vs BICR

		BICR	
		Event	No Event
Investigator	Event	$a = a_1 + a_2 + a_3$	b
	No Event	c	d

a1: number of agreements on timing and occurrence of event;
 a2: number of times agreement on event but INV declares event later than BICR;
 a3: number of times agreement on event but INV declares event earlier than BICR;
 $N = a + b + c + d$.

The timing agreement of event is defined as a window of ± 7 days.

The following measure of discordance will be calculated for each treatment arm:

- Total Event Discrepancy Rate: $(b+c) / N$
- Early Discrepancy Rate (EDR): $(a_3+b) / (a+b)$
- Late Discrepancy Rate (LDR): $(a_2+c) / (a_2+a_3+b+c)$
- Overall Discrepancy Rate: $(a_2+a_3+b+c) / N$

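### Two footnotes of the pre-Amendment 2 schedule conflict on imaging after site-declared progression that BICR has not confirmed; following footnote 6 would censor BICR PFS informatively

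*Protocol*

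**What the plan says.** Footnote 6 of the Schedule of Activities covers follow-up for PFS and OS and divides patients by why treatment ended. Those who stop without progression keep 8-weekly scans until progression is documented. For the others: "Patients who have discontinued study treatment due to progressive disease should be followed for survival every 12 weeks via telephone call until study end". Neither sentence says whose reading of progression counts.

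Footnote 31, on tumor assessments, says that scans "will be conducted every 8 weeks until documented disease progression as assessed by BICR regardless of subsequent anti-cancer therapy". SAP 6.1.2.1 describes imaging "every 8 weeks until disease progression regardless of initiation of subsequent anti-cancer therapy", and that section defines progression as progression by BICR.

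The decision to stop treatment rests with the site: "study treatment may continue until PD as assessed by the investigator" (Protocol Summary, Study Treatments; likewise Sections 3.1.2 and 6.5).

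The primary PFS rule censors at the last adequate scan once new anti-cancer therapy starts. SAP 6.2.2.2 adds a sensitivity analysis "with initiation of subsequent anti-cancer therapies not used as a censoring reason".

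Amendment 2 retired this schedule and its footnotes, but only after the final analysis, so they were in place while the primary PFS data were collected.

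**The concern.** A patient whose site declares progression, and who stops treatment for it, may have no progression on central review. Footnote 31 and the SAP keep her on 8-weekly scans. Footnote 6, by contrasting her with patients who stopped without progression, can be read as moving her to telephone contact only.

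If scanning stops there, BICR has no further images on which to date progression, and she is censored at her last adequate scan. That censoring is informative, because she is probably close to BICR progression. In an open-label trial the frequency of early site calls may differ by arm, and the BICR hazard ratio then moves. BICR was made the primary reading in order to limit that influence.

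The analysis that does not censor at new therapy is more exposed. It depends on scans taken after site-declared progression, and under footnote 6 those scans would not exist.

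**Working it through.** **1. The passages side by side, for a patient with site progression, no BICR progression, and treatment stopped**

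- Footnote 6: survival call every 12 weeks. Imaging is not mentioned.
- Footnote 31: scan every 8 weeks until BICR progression, including after new therapy.
- SAP 6.1.2.1: as footnote 31.
- Schedule table: CT/MRI is marked in the Follow-up column. That column's heading refers to footnote 6 and the CT/MRI row refers to footnote 31, so the mark does not settle the question.

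**2. The plan's own PFS figure**

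Protocol 9.1: "325 PFS events by BICR assessment within each comparison will provide 93% power to detect a HR of 0.6". SAP 5.1.1 sets the one-sided levels by "allocating 0.0115 alpha to each of the two OS comparisons and 0.001 to each of the two PFS comparisons". The interim look comes when "at least 267 (82%) of the 325 PFS events for each of the PFS comparisons have been documented" (SAP 5.1.2).

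- Fixed design: power = Φ(√(D/4)·|ln HR| − z). With D = 325, HR = 0.6 and z = 3.090: √81.25 × 0.5108 = 4.605; 4.605 − 3.090 = 1.514; Φ(1.514) = 0.935.
- Two looks (267/325, Lan-DeMets O'Brien-Fleming): interim boundary 3.4474, power 0.933. Both agree with the documents.

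**3. Room for lost events**

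- Patients per comparison: 550 × 2/3 ≈ 367. Required share with a BICR event: 325/366.7 = 88.6%. That leaves about 42 patients for every kind of censoring.
- Expected events at 31 months under HR 0.6, with uniform 19-month accrual assumed: 345 with no drop-out, 321 if the 15% drop-out is annual, 293 if 15% are lost outright.

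The analysis is event-driven, so lost events first delay the cut-off. They cost power only if 325 cannot be reached.

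**4. Size of the effect, by simulation**

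From the documents: medians 3.5 and 5.8 months, about 183 patients per arm, 8-weekly scans. Assumed: exponential times, 15% drop-out per 12 months, and site progression one scan before BICR progression in a stated share of patients whose BICR progression falls at scan 2 or later. Of these, 50% or 80% start new therapy before the next scan. Deaths, repeat scans and expedited central review are not modelled.

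BICR events per comparison, same rate in both arms, 50% starting new therapy:

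| Early site calls | Footnote 31 | Footnote 6 |
|---|---|---|
| 0% | 313 | 313 |
| 10% | 302 | 291 |
| 20% | 292 | 269 |
| 30% | 280 | 247 |

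With equal rates the hazard ratio stays near 0.60 throughout. With unequal rates (50% new therapy):

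| Early calls, PLD / avelumab | Footnote 6 | Footnote 31, censored at new therapy | Footnote 31, new therapy ignored |
|---|---|---|---|
| 10% / 20% | 0.559 | 0.581 | 0.603 |
| 20% / 10% | 0.638 | 0.615 | 0.597 |

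- Primary analysis, footnote 6 against 31: 0.581 − 0.559 = 0.022 and 0.638 − 0.615 = 0.023. With 80% starting new therapy it is about 0.01.
- Analysis ignoring new therapy: 0.603 − 0.559 = 0.044 and 0.638 − 0.597 = 0.041.

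An independent repeat gave 0.552, 0.575 and 0.597 for the first row and 0.651, 0.629 and 0.609 for the second: the same shifts of about 0.02 and 0.04.

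**The case against.** The strongest reply is that footnote 6 adds a survival call and never says that imaging ends, so a site could follow both footnotes. That is a possible reading, and it is why the conflict is conditional. But footnote 6 gives scans expressly to one group and calls to the other, and no text says which footnote prevails.

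Second, the wording that treatment stops at investigator progression is Amendment 2 text. The amendment log indicates that some patients could previously stay on treatment after a first site progression, and that PLD could resume in Arm B if progression was not confirmed. Amendment 1 added an expedited BICR of site-declared progression, and footnote 31 lists progression among the findings that prompt a repeat scan after at least 4 weeks. All of this stands and would reduce the effect. The earlier operating text is no longer visible, and one repeat scan is not scanning until BICR progression.

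Third, the SAP already offers partial checks: investigator-assessed PFS, discordance rates by arm, a plot of planned against actual scan days, and analyses counting all deaths as events. These stand too, but none counts patients whose imaging stopped after unconfirmed site progression.

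A reader might infer that such a patient can never have BICR progression, or that SAP Table 10 must class her as still in follow-up without an event. The documents support neither. She may have been scanned under footnote 31. Table 10 can also place her under new therapy, an event after missed scans, withdrawal or loss to follow-up. A death after at most one missed scan, before any new therapy, counts as an event.

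**Conclusion.** The conflict is real and concerns how a primary endpoint was ascertained. If sites followed footnote 6, patients with unconfirmed site progression and no new therapy were informatively censored in the primary PFS analysis, and the analysis that ignores new therapy lacked scans it needs.

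The effect on the primary hazard ratio is small: about 0.01 to 0.02 under assumed rates of 10% against 20%, in either direction, and essentially nil if the rates are equal. For the analysis ignoring new therapy it is about 0.04. These figures rest on assumed discordance rates, an assumed lag of one scan and an assumed uptake of new therapy. The safeguards omitted from the model would be expected to reduce them.

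A reader might conclude that the completed PFS result lost events or is biased. The documents do not show that: they report neither which footnote sites followed nor how often the readings disagreed. Nor can the whole shift away from 0.60 in the unequal-rate table be laid to footnote 6. About half of it remains under footnote 31, because the primary rule censors at new therapy anyway. The 325 events and 93% power are unaffected as design figures.

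**What to change.** Reconcile footnote 6 with footnote 31 and SAP 6.1.2.1, so that 8-weekly scans continue until progression is documented by BICR and survival calls do not replace them before then. This restates what two of the three passages already require.

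Because the footnotes were retired only after the final analysis, three steps apply to the completed data:

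- State which footnote governed imaging after site progression without BICR progression.
- Report by arm how many patients had investigator progression, no BICR progression and no later scan.
- Add one exploratory PFS sensitivity analysis counting those patients as events at the next planned scan date.

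The cost is one table and one extra run. If the wording were used prospectively, it would also mean further scans for a few patients.
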